7.2.2. Assessment of Severity

The severity of AEs will be graded using the Division of AIDS (DAIDS) Table for Grading the Severity of Adult and Pediatric Adverse Events Toxicity Grading Scale, Version 2.1 (corrected, July 2017). For each episode, the highest grade attained should be reported as defined in the Toxicity Grading Scale. The DAIDS scale is available at:

<https://rsc.niaid.nih.gov/sites/default/files/daidsgradingcorrectedv21.pdf>

7.3. Investigator Reporting Requirements and Instructions

7.3.1. Requirements for Collection Before Study Drug Initiation

After informed consent, but before initiation of study drug, the following types of events must be reported on the applicable eCRFs: all SAEs and any AEs that are related to protocol-required procedures.

7.3.2. Adverse Events

Following initiation of study drug, collect all AEs, regardless of cause or relationship, until 30 days after last administration of study drug and report the AEs on the eCRFs as instructed.

All AEs and clinically significant laboratory abnormalities should be followed until resolution or until the AE is stable, if possible. Gilead may request that certain AEs be followed beyond the protocol-defined follow-up period.

7.3.3. Serious Adverse Events

All SAEs, regardless of cause or relationship, that occur after the participant first consents to participate in the study (ie, signing the ICF) and throughout the duration of the study, including the posttreatment follow-up visit, must be reported on the applicable eCRFs and to Gilead Patient Safety as instructed below in this section. This also includes any SAEs resulting from protocol-associated procedures performed after the ICF is signed.

Any SAEs and deaths that occur after the posttreatment follow-up visit but within 30 days of the last dose of study drug, regardless of causality, should also be reported.

Investigators are not obligated to actively seek SAEs after the protocol-defined follow-up period; however, if the investigator learns of any SAEs that occur after the protocol-defined follow-up period has concluded and the event is deemed relevant to the use of study drug, the investigator should promptly document and report the event to Gilead Patient Safety.

Instructions for reporting SAEs are described in Section [7.4.1](#).

7.3.4. Study Drug Special Situations Reports

All study drug SSRs that occur from study drug initiation and throughout the duration of the study, including the posttreatment follow-up visit, must be reported to Gilead Patient Safety (Section [7.4.2](#)). Adverse events and SAEs resulting from SSRs must be reported in accordance with the AE and SAE reporting guidance (Section [7.3](#)).

7.3.5. Concomitant Medications Reports

7.3.5.1. Gilead Concomitant Medications Special Situations Report

Special situations reports involving a Gilead concomitant medication (not considered study drug), that occur after the participant first consents to participate in the study (ie, signing of the ICF) and throughout the duration of the study, including the posttreatment follow-up visit, must be reported to Gilead Patient Safety utilizing the paper SSR (Section [7.4.2.2](#)).

7.3.5.2. Non-Gilead Concomitant Medications Report

Special situations involving non-Gilead concomitant medications do not need to be reported on the SSR form; however, for special situations that result in AEs because of a non-Gilead concomitant medication, the AE should be reported on the AE eCRF.

Any inappropriate use of concomitant medications prohibited by this protocol should not be reported as “misuse,” but may be more appropriately documented as a protocol deviation.

All clinical sequelae in relation to these SSRs will be reported as AEs or SAEs at the same time using the AE eCRF and/or the SAE eCRF. Details of the symptoms and signs, clinical management, and outcome will be reported, when available.

7.4. Reporting Process for Serious Adverse Events and Special Situations Reports

7.4.1. Serious Adverse Event Reporting Process

For fatal or life-threatening events, copies of hospital case reports, autopsy reports, and other documents are also to be transmitted by email or fax when requested and applicable.

Transmission of such documents should occur without personal participant identification, maintaining the traceability of a document to the participant identifiers.

Additional information may be requested to ensure the timely completion of accurate safety reports.

Any medications necessary for treatment of the SAE must be recorded onto the concomitant medication section of the participant’s eCRF and the SAE narrative section of the Safety Report Form eCRF.

7.4.1.1. Electronic Serious Adverse Event Reporting Process

Site personnel will record all SAE data on the applicable eCRFs and from there transmit the SAE information to Gilead Patient Safety within 24 hours of the investigator’s knowledge of the event from the time of the ICF signature throughout the duration of the study, including the protocol-required posttreatment follow-up period.

If for any reason it is not possible to record and transmit the SAE information electronically, record the SAE on the paper SAE reporting form and transmit within 24 hours to:

Gilead Patient Safety

Email: PPD

or

Fax: PPD

If an SAE has been reported via a paper form because the eCRF database has been locked, no further action is necessary. If the database is not locked, any SAE reported via paper must be transcribed as soon as possible on the applicable eCRFs and transmitted to Gilead Patient Safety.

7.4.2. Special Situations Reporting Process

7.4.2.1. Electronic Special Situations Reporting Process for Study Drug

Site personnel will record all SSR data on the applicable eCRFs and from there transmit the SSR information within 24 hours of the investigator's knowledge to Gilead Patient Safety from study drug initiation throughout the duration of the study, including the protocol-required posttreatment follow-up period.

If for any reason it is not possible to record and transmit the SSR information electronically, record the SSR on the paper SSR form and transmit within 24 hours to:

Gilead Patient Safety

Email: PPD

or

Fax: PPD

If an SSR has been reported via a paper form because the eCRF database has been locked, no further action is necessary. If the database is not locked, any SSR reported via paper must be transcribed as soon as possible on the applicable eCRFs and transmitted to Gilead Patient Safety.

See Section [7.4.2.2](#) for instructions on reporting special situations with Gilead concomitant medications.

7.4.2.2. Reporting Process for Gilead Concomitant Medications

Special situations that involve Gilead concomitant medications that are not considered study drug must be reported within 24 hours of the investigator's knowledge of the event to Gilead Patient Safety utilizing the paper SSR form and transmitted to:

Gilead Patient Safety

Email: PPD

or

Fax: PPD

Any inappropriate use of concomitant medications prohibited by this protocol should not be reported as "misuse," but may be more appropriately documented as a protocol deviation.

Special situations involving non-Gilead concomitant medications do not need to be reported on the SSR form; however, special situations that result in AEs because of a non-Gilead concomitant medication, must be reported on the AE eCRF.

7.4.2.3. Pregnancy Reporting Process

The investigator should report pregnancies identified after initiation of study drug to 30 days after the last study dose in participants and/or pregnancies in partner resulting from exposure to sperm from a participant in study period in which contraceptive measures are needed.

Pregnancies should be reported to Gilead Patient Safety within 24 hours of becoming aware of the pregnancy using the pregnancy report form. Contact details for transmitting the pregnancy report form are as follows:

Gilead Patient Safety

Email: PPD

or

Fax: PPD

The pregnancy itself is not considered an AE, nor is an induced elective abortion to terminate a pregnancy without medical reasons.

All other premature terminations of pregnancy (eg, a spontaneous abortion, an induced therapeutic abortion because of complications or other medical reasons) must be reported within 24 hours as an SAE, as described in Section 7.4.1. The underlying medical reason for this procedure should be recorded as the AE term.

A spontaneous abortion is always considered to be an SAE and will be reported as described in Section 7.4.1. Furthermore, any SAE occurring as an adverse pregnancy outcome after the study must be reported to the Gilead Patient Safety.

The participant should receive appropriate monitoring and care until the conclusion of the pregnancy. The outcome of the pregnancy/partner pregnancy should be reported to Gilead Patient Safety using the pregnancy outcome report form. If the end of the pregnancy/partner pregnancy occurs after the study has been completed, the outcome should be reported directly to Gilead Patient Safety. Gilead Patient Safety contact information is as follows: email: [contact] and [contact].

Refer to Appendix [11.4](#) for Pregnancy Precautions, Definition for Childbearing Potential, and Contraceptive Requirements.

7.5. Gilead Reporting Requirements

Depending on relevant local legislation or regulations, including the applicable US FDA Code of Federal Regulations, the EU Regulation 536/2014 and relevant updates, and other country-specific legislation or regulations, Gilead may be required to expedite to worldwide regulatory agencies reports of SAEs, which may be in the form of line listings, serious adverse drug reactions, or suspected unexpected serious adverse reactions. In accordance with the EU Regulation 536/2014, Gilead or a specified designee will notify worldwide regulatory agencies and the relevant IEC in concerned Member States of applicable suspected unexpected serious adverse reactions as outlined in current regulations.

Assessment of expectedness for SAEs will be determined by Gilead using reference safety information specified in the IB or relevant local label as applicable.

All investigators will receive a safety letter notifying them of relevant suspected unexpected serious adverse reaction reports associated with any study drug. The investigator should notify the IRB or IEC of suspected unexpected serious adverse reaction reports as soon as is practical, where this is required by local regulatory agencies, and in accordance with the local institutional policy.

7.6. Clinical Laboratory Abnormalities and Other Abnormal Assessments as Adverse Events or Serious Adverse Events

Laboratory abnormalities without clinical significance are not to be recorded as AEs or SAEs. However, laboratory abnormalities (eg, clinical chemistry, hematology, urinalysis) that require medical or surgical intervention or lead to study drug interruption, modification, or discontinuation must be recorded as an AE, as well as an SAE, if applicable. In addition, laboratory or other abnormal assessments (eg, vital signs) that are associated with signs and/or symptoms must be recorded as an AE or SAE if they meet the definition of an AE or SAE as described in Sections [7.1.1](#) and [7.1.2](#). If the laboratory abnormality is part of a syndrome, record the syndrome or diagnosis (eg, anemia), not the laboratory result (ie, decreased hemoglobin).

Severity should be recorded and graded according to the DAIDS for Grading the Severity of Adult and Pediatric Adverse Events, Version 2.1 (corrected, July 2017). For AEs associated with laboratory abnormalities, the event should be graded on the basis of the clinical severity in the context of the underlying conditions; this may or may not be in agreement with the grading of the laboratory abnormality.

The DAIDS scale is available at:

<https://rsc.niaid.nih.gov/sites/default/files/daidsgradingcorrectedv21.pdf>

7.7. Toxicity Management

7.7.1. Obeldesivir

All clinical and clinically significant laboratory toxicities will be managed according to the guidelines described below.

The Gilead medical monitor should be consulted prior to study drug discontinuation when medically feasible. Before discontinuation of study drug for AEs or laboratory abnormalities, an assessment of the participant's medical situation should be made by the investigator.

7.7.1.1. Laboratory Events Meeting Discontinuation Criteria

Laboratory events meeting discontinuation criteria are discussed in Section [3.3.1.1](#).

7.7.1.2. Grades 1 and 2 Laboratory Abnormality or Clinical Event

Continue study drug at the discretion of the investigator.

7.7.1.3. Grade 3 Laboratory Abnormality or Clinical Event

For a Grade 3 clinically significant laboratory abnormality or clinical event, study drug may be continued if the event is considered to be unrelated to study drug.

For a Grade 3 clinically significant laboratory abnormality or clinical event, confirmed by repeat testing, that is considered to be related to study drug, **the participant will be discontinued from study drug**. The participant should be managed according to local practice.

Additionally, participants who have an eGFR < 50 mL/min/1.73 m² by Bedside Schwartz formula will be discontinued from study drug whether considered related to the study drug or not (refer to Section [3.3.1.1](#)).

Recurrence of laboratory abnormalities considered unrelated to study drug may not require permanent discontinuation but requires discussion with the Gilead medical monitor.

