3.3. Protocol-Specific Discontinuation Criteria

3.3.1. Criteria for Early Discontinuation for the Individual Participants

3.3.1.1. Criteria for Early Discontinuation for the Individual Participants From Study Intervention

Study drug will be discontinued in the following instances:

- Any SAE suspected to be related to study drug.
- Any \geq Grade 3 AE suspected to be related to study drug.
- An AE, or worsening of clinical condition requiring clinical intervention, that would, in the judgment of the investigator, affect assessments of clinical status to a significant degree.
- Any \geq Grade 3 clinically significant laboratory abnormality (if confirmed by repeat testing) suspected to be related to study drug.
- eGFR < 50 mL/min/1.73 m² (≥ 1 year of age) using the Bedside Schwartz formula.
- Alanine aminotransferase (ALT) $\geq 5 \times$ upper limit of normal (ULN).
- Bilirubin $\geq 2 \times$ ULN ($\geq 3 \times$ ULN for participants with Gilbert's syndrome).
- Unacceptable toxicity, as defined in Section [7.7](#), or toxicity that, in the judgment of the investigator, compromises the ability to continue study-specific procedures or is considered not to be in the participant's best interest.
- Participant request to discontinue for any reason.
- Participant noncompliance with the study protocol.
- Pregnancy (refer to Appendix [11.4](#)).
- Discontinuation of the study by sponsor.
- Creatinine level above the thresholds described in [Table 3](#) if < 1 year of age.

Table 3. Creatinine Value Cutoff by Age Group

Gestational age	Chronological age	Creatinine Value Cutoff in mg/dL
≥ 24 to ≤ 27 weeks	0 to < 28 days	CC1
≥ 28 to ≤ 29 weeks	0 to < 14 days	CC1
≥ 30 to < 32 weeks	0 to < 7 days	CC1
	≥ 7 days to 1 month	CC1
	≥ 1 to < 2 months	CC1
	≥ 2 months to < 1 year	CC1
≥ 32 weeks	0 to < 2 days	CC1
	≥ 2 to < 7 days	CC1
	≥ 7 days to 2 months	CC1
	≥ 2 months to < 1 year	CC1

* Creatinine values CC1

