7.7.1.4. Grade 4 Laboratory Abnormality or Clinical Event

For a Grade 4 clinically significant laboratory abnormality or clinical event, confirmed by repeat testing, that is considered to be related to study drug, **the participant will be discontinued from study drug**. The participant should be managed according to local practice. The participant should be followed as clinically indicated until the laboratory abnormality returns to baseline or is otherwise explained, whichever occurs first. A clinically significant Grade 4 laboratory abnormality that is not confirmed by repeat testing should be managed according to the algorithm for the new toxicity grade.

Study drug may be continued without dose interruption for a clinically nonsignificant Grade 4 laboratory abnormality (eg, Grade 4 creatine kinase elevation after strenuous exercise or triglyceride elevation that is nonfasting or that can be medically managed) or a clinical event considered unrelated to study drug.

Treatment-emergent toxicities will be noted by the investigator and brought to the attention of the Gilead medical monitor, and the appropriate course of action will be discussed and decided. Whether or not considered treatment-related, all participants experiencing AEs must be monitored periodically until symptoms subside, any abnormal laboratory values have resolved or returned to baseline levels or they are considered irreversible, or until there is a satisfactory explanation for the changes observed.

Any questions regarding toxicity management should be directed to the Gilead medical monitor.

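### Protocol Sections 3.3.1.1 and 7.7.1.2 to 7.7.1.4 do not state the same drug-stopping rules, and nothing says which section governs

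*Protocol*

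**What the plan says.** Section 3.3.1.1 opens its list with a mandate: "Study drug will be discontinued in the following instances". Three kinds of item on that list matter here.

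- Clinical events: any AE at or above "Grade 3 AE suspected to be related to study drug". No confirmation is asked for.
- Laboratory findings in general: Grade 3 or higher, with the qualifiers "clinically significant laboratory abnormality (if confirmed by repeat testing) suspected to be related to study drug".
- Fixed limits: ALT at 5 x ULN or above; bilirubin at 2 x ULN or above (3 x ULN in Gilbert's syndrome); eGFR below 50 mL/min/1.73 m² from 1 year of age; creatinine above the Table 3 cutoffs under 1 year. None of these is made conditional on causality, repeat testing or clinical significance.

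Section 7.7 sorts events by toxicity grade.

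- Section 7.7.1.1 says that the laboratory events meeting discontinuation criteria are dealt with in Section 3.3.1.1.
- Section 7.7.1.2 leaves continuation at Grades 1 and 2 to the investigator.
- Section 7.7.1.3 covers Grade 3 laboratory abnormalities and clinical events together: "study drug may be continued if the event is considered to be unrelated to study drug". The stop applies when the event is "confirmed by repeat testing, that is considered to be related to study drug". One limit, eGFR, is then singled out as stopping drug whether related or not.
- Section 7.7.1.4 uses the same stop condition at Grade 4 and adds: "Study drug may be continued without dose interruption for a clinically nonsignificant Grade 4 laboratory abnormality". It also allows continuation for a clinical event judged unrelated.

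**The concern.** An investigator with a raised ALT or bilirubin result can consult either section in good faith. One gives an unconditional stop. The other gives a grade-based rule that turns on causality or clinical significance. For a related clinical event, one section requires a stop at once and the other appears to wait for a repeat test.

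The first thing at stake is participant safety: two children with the same finding could be managed differently. Section 1.5 relies on clearly defined discontinuation parameters as part of its risk mitigation. The data are affected as well. Exposure (Section 8.6.1) would depend on the section a site followed. Section 7.6 also requires a laboratory abnormality that leads to discontinuation to be recorded as an AE, so some treatment-emergent AE counts could shift too.

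**Working it through.** This is a comparison of text. The protocol gives no figure to reproduce.

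**Part 1: fixed laboratory limits**

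| Finding | Section 3.3.1.1 | Section 7.7 |
|---|---|---|
| ALT or bilirubin at its limit, if Grade 1 or 2 | Stop | Investigator discretion (7.7.1.2) |
| The same, if Grade 3 and judged unrelated | Stop | May continue (7.7.1.3) |
| The same, if Grade 4 and judged clinically nonsignificant | Stop | May continue (7.7.1.4) |
| Creatinine above Table 3, under 1 year | Stop | Same grade-based routes |
| eGFR below 50, from 1 year of age | Stop | Stop, related or not (7.7.1.3) |
| Grade 3 or 4 laboratory abnormality, clinically significant, confirmed and related | Stop | Stop |

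The last two rows agree. The first four do not agree on the wording. The document does not say which toxicity grade each limit corresponds to; it only cites the grading table. The comparison does not need that mapping, because Section 7.7 has a continuation route at each grade. What depends on the grade is which route applies.

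Section 7.7.1.1 bears on all four of those rows, because these limits are laboratory discontinuation criteria. It locates the criteria in Section 3.3.1.1. It does not say that they override the permissions that follow, and Section 7.7.1.3 restates the override for eGFR only.

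**Part 2: related clinical events of Grade 3 or higher**

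- Section 3.3.1.1: stop if related. Repeat testing appears only in the separate laboratory item.
- Sections 7.7.1.3 and 7.7.1.4: stop if related and confirmed by a repeat test, with laboratory abnormalities and clinical events in the same sentence.
- A related clinical event with no repeat test is therefore a mandatory stop in one section and meets no stated stop condition in the other. Section 7.7 does not say that drug may continue in that case.
- Section 7.7.1.1 speaks of laboratory events only, so it does not reach this mismatch.

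**How much of the course is exposed**

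Inputs: twice-daily dosing for 5 days (Section 5.4), and first on-treatment chemistry sample at Day 3 (Table 5, Section 11.6).

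- Course: 5 x 2 = 10 doses.
- Assume a morning start on Day 1, a morning sample on Day 3 taken after that morning's dose, and an immediate result.
- Doses left: 1 (Day 3 evening) + 2 (Day 4) + 2 (Day 5) = 5, and 5/10 = 50%.
- Any delay in the result lowers this. If the sample preceded the Day 3 morning dose, that dose would be added: 5 + 1 = 6.

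This bounds what is at stake for one child. It says nothing about how often the two sections would lead to different actions.

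**The case against.** The strongest reply is that the sections can be read together. Section 3.3.1.1 is mandatory, Section 7.7 is permissive, and a site that obeys the mandate breaches nothing. Section 7.7.1.1 comes before the grade-based rules and sends laboratory discontinuation criteria to Section 3.3.1.1. The eGFR sentence also cites Section 3.3.1.1 and can be read as a reminder. This has force. For the laboratory limits it reduces the problem to an unresolved inconsistency. It does not remove it, because no sentence gives Section 3.3.1.1 precedence and restating only one of several unconditional limits invites doubt about the rest.

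A reader might infer several stronger things that the document does not support.

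- *That Section 7.7 lets a child continue after a related Grade 3 or 4 clinical event.* It does not. Its permissions for clinical events at those grades are limited to unrelated ones. The fault is a stop condition that differs, possibly a loosely placed modifier, since repeat testing fits few clinical events.
- *That the ALT, bilirubin and creatinine limits depend on causality.* The eGFR sentence suggests this to some readers but does not say it.
- *That the creatinine mismatch affects children now being dosed.* It applies under 1 year. Section 5.4 sets doses only for Cohorts 1 and 2, who are at least 6 years old. It becomes relevant once younger cohorts open.
- *That a planned summary of discontinuations due to AEs is compromised.* The protocol names no such summary.

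There is also a safeguard. Section 7.7.1 asks for the medical monitor to be consulted before discontinuation where feasible, and Section 7.7.1.4 brings treatment-emergent toxicities to the monitor for a decision. That should limit differences between sites. It does not settle the rule, because the monitor works from the same two texts.

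**Conclusion.** The point holds in two parts. First, the unconditional ALT and bilirubin limits (and the creatinine limits for later cohorts) sit beside grade-based continuation rules that do not except them; the pointer in Section 7.7.1.1 softens this without resolving it. Second, the stop condition for related clinical events of Grade 3 or higher differs between the sections on repeat testing, and no cross-reference covers it.

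The rules do agree for confirmed, related, clinically significant laboratory abnormalities of Grade 3 or higher, and for eGFR from 1 year of age. The consequence is possible inconsistent handling of individual children and of their exposure. The figure of 5 of 10 doses is an upper bound under the timing assumptions shown, not an expected loss. The sample-size calculation is not affected. This should be corrected, and the correction is one of wording. No view is taken here on which clinical rule is right.

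**What to change.** Reconcile the passages in the next amendment:

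1. State each stopping criterion once, and have the other section refer to it with a sentence saying which section governs.
2. State whether repeat testing applies to clinical events or only to laboratory findings.
3. State whether the ALT, bilirubin and creatinine limits act regardless of causality, as eGFR is said to do.

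The sponsor's clinical team decides the content of each rule. The cost is protocol text and notice to sites, with no added procedures or samples. The protocol already foresees amendments for the younger cohorts (Sections 5.4, 6.3.5 and 11.6). The creatinine wording should be settled before infants are enrolled.
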